## 2.2 Study Design and Dose Rationale

### 2.2.1 Study Design

This study is an extension study conducted as an open-label, multicenter study in RA patients who have completed studies RAJ1, RAJ3, or RAJ4.

Patients who meet all the inclusion criteria and do not fall under any of the exclusion criteria will receive oral ASP015K 100 mg QD after breakfast as the starting dose. For subjects who have been receiving ASP015K at a dose of 50 mg/day in Japan, the dose will be increased to 100 mg/day after the NDA approval in Japan. Any subjects for whom the dose cannot be increased should be withdrawn from the study. Subjects who have no safety problems but show lack of efficacy may later increase the dose to 150 mg/day. Only in Korea and Taiwan, the dosage may be reduced from 100 mg/day or 150 mg/day to 50 mg/day at the discretion of the investigator or sub-investigator. The starting dose for subjects who transferred from study RAJ1 is 50 mg/day. For subjects who transferred from study RAJ1 and are continuing to receive 50 mg/day, treatment extension using a dose of 50 mg/day should be allowed when the investigator or sub-investigator considers a dose increase to be inappropriate in terms of safety and treatment extension with a dose of 50 mg/day to provide greater therapeutic benefit for the treatment of RA.

This study will be conducted as a post-marketing clinical study up to a maximum of 6 months after the NDA approval in Japan. (After the NDA approval in Japan, the post-marketing clinical study will be ended once the study drug is available in the clinical sites as a commercially available product. The planned study period will be a maximum of 6 months after the NDA approval in Japan). In Korea and Taiwan, this study will continue as a clinical study after the NDA approval in Japan. The duration of treatment will differ depending on the subject. To prevent purposeless continuation of dosing without effect, the investigator or sub-investigator will assess each subject for efficacy and safety at each visit, confirm the appropriateness of continued administration for each individual, and decide whether or not to continue dosing.

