### 2.2.2 Dose Rationale

[Rationale for setting dose]

The starting dose for this extension study will be 100 mg/day, to be increased to 150 mg/day at the time of dose escalation.

The dose levels for study RAJ1 have been set at ASP015K 0 mg/day (placebo), 25 mg/day, 50 mg/day, 100 mg/day, and 150 mg/day. As a result, the ACR20 response rate at Week 12 (or early termination) in ASP015K groups receiving 50 mg/day or more showed a statistically significant increase over the placebo group; the increase in the ACR20 response rate was dose dependent up to 150 mg. Compared with the placebo group, a significant and dose-dependent decrease was also found in the reduction of DAS28-CRP score at Week 12 (or early termination) in the 50 mg, 100 mg, and 150 mg groups. A comparison of the

- CONFIDENTIAL -

interview forms of Enbrel®, Simponi®, Xeljanz®, and Humira® showed that ASP015K at a dose of 100 mg or higher was found to have the same efficacy as the other drugs at their approved doses. Based on these results, the dose levels for the Phase III studies (RAJ3 and RAJ4) have been set at ASP015K 100 mg/day and 150 mg/day.

Due to safety considerations, the starting dose for this extension study has been set at 100 mg/day, which was the lower of the two doses set for the Phase III studies. For subjects who have no safety problems but show a lack of efficacy, the dosage may later be increased from 100 mg/day to 150 mg/day. However, in subjects who transferred from study RAJ1, the extension study is performed using a dosage design with 50 mg/day as the starting dose and 100 mg/day as the increased dose. Subjects who completed study RAJ1 and are continuing the treatment with ASP015K at a dose of 50 mg/day shall be included in the clinical study under the protocol ver. 2.0/ver. 3.0; later, when the study drugs after the change in specifications become available for use, the dose shall be increased to 100 mg/day, with the exception of the subjects for whom the investigator or sub-investigator considers a dose increase to be inappropriate in terms of safety and treatment extension with a dose of 50 mg/day to provide greater therapeutic benefit for the treatment of RA. If treatment is to be continued at a dose of 50 mg/day, the reason for this decision must be recorded in the medical record.

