### 7.1 Sample Size

Approximately 800 treated patients

[Rationale for the sample size]

The sample size estimation is based on the number of subjects who have completed the preceding study of ASP015K (Study 015K-CL-RAJ1) and participate in this extension study (201 subjects), the planned number of subjects in Study 015K-CL-RAJ3 excluding those in the reference group (300 subjects), and the planned number of subjects in Study 015K-CL-RAJ4 (510 subjects).

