**SYNOPSIS**

Title of Study	Phase IIb Extension Study of ASP015K – Open-Label Extension Study in Rheumatoid Arthritis Patients Who Have Completed Phase IIb Study of ASP015K – (Protocol Number: 015K-CL-RAJ2)
Study Objectives	This is an extension study conducted in RA patients who have completed the Phase IIb Study of ASP015K [015K-CL-RAJ1] (hereinafter referred to as study RAJ1) to investigate the safety and efficacy of long-term administration of ASP015K. Another objective of this study is to devise rescue measures for providing the active drug to patients who participated in the Phase IIb Study of ASP015K, as described in “Guidelines on methodology for clinical assessment of antirheumatic drugs” (PFSB Notification No. 0217001, dated 17 February, 2006).
Design and Methodology	This study is an extension of study RAJ1 conducted as an open-label multicenter study in RA patients who completed study RAJ1.  Patients who meet all of the inclusion criteria and do not fall under any of the exclusion criteria will be registered and will receive oral ASP015K 50 mg QD after breakfast as the starting dose. Subjects who have no safety problems but show lack of efficacy may later increase the dose to 100 mg/day. After the dosage increase, the dosage may be reduced from 100 mg/day to 50 mg/day at the discretion of the investigator or sub-investigator. The dose level will be redetermined after the results of the dose finding study (study RAJ1) have been obtained.  Because this study will end at the point in time where the Phase III study begins, the duration of treatment with the study drug will differ depending upon the subject (planned maximum duration of treatment: 132 weeks). To prevent purposeless continuation of dosing without effect, the investigator or sub-investigator will assess each subject for efficacy and safety at each visit, confirm the appropriateness of continued administration for each individual, and decide whether or not to continue dosing.

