
Test Drug  Mode of Administration:  Dose:  Duration of Treatment:
	
Test drug: ASP015K 10 mg and 30 mg tablets  Dose: (starting dose) 50 mg/day, (escalated dose) 100 mg/day  The starting dose will be 50 mg/day.  The dose may be increased to 100 mg QD will be permitted at the point in time as the following 2 conditions are met.
 
 
1) When the DAS28-ESR score is 3.2 or higher (corresponding to moderate disease activity or high disease activity) on the study visit day specified in the protocol (at 2 or more consecutive visit days up to Week 12)
 
2) When the investigator or sub-investigator judges there to be no problem with safety for the subject in the assessment performed on the study visit day on which the DAS28-ESR of 3.2 score or higher was exhibited
 
 
Moreover, after dose escalation, the dose may again be reduced from 100 mg/day to 50 mg/day at the discretion of the investigator or sub-investigator on the visit day specified in the protocol. The investigator or sub-investigator will decide whether or not to reduce the dosage on the basis of the following criterion.
 
 
• If an AE with an NCI-CTCAE grade classification of Grade 2 or higher has developed.
 
 
Mode of administration: To be orally administered QD after breakfast. The first dose should be given at each study center on the day of the Week 0 visit after all of the necessary assessments and tests have been completed.
 
Duration of treatment: Because this study will end at the point in time where the Phase III study begins, the duration of treatment will differ depending upon the subject (planned maximum duration of treatment: 132 weeks). To

- CONFIDENTIAL -

	prevent purposeless continuation of dosing without effect, the investigator or sub-investigator will assess each subject for efficacy and safety at each visit, confirm the appropriateness of continued administration for each individual, and decide whether or not to continue dosing.
Comparative drug Mode of Administration: Dose: Duration of Treatment:	Not applicable.

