7.3.1 Exposure

[Analysis Set: SAF]

Duration of exposure during RAJ2 will be summarized in two ways.

- Descriptive statistics will be presented
- Exposure time for overall period will be categorized according to the following categories:
 - \circ 0 1 month
 - \circ 1 <- 3 months
 - \circ 3 <- 6 months
 - 6 <- 12 months
 - 12 <- 24 months
 - o 24 <- 36 months
 - 36 <- 48 months
 - 48 <- 60 months
 - o 60 <- 72 months
 - 72 <- 84 months
 - o 84 months <

Counts and percentages of subjects in each category will be summarized.

In addition to this, the following information on drug exposure will be presented:

- Number and percent of subject with dose increase/ dose decrease/ drug suspension/ drug interruption
- Number of experience for dose increase/ dose decrease/ drug suspension/ drug interruption per subject
- Duration from First Study Drug Taken up to First Dose Change to ASP015K 100 mg (from RAJ1) or 150 mg (from RAJ3/RAJ4)
- Maximum Dose of Study Drug (ASP015K 50 mg/ 100 mg/ 150 mg)

The following Kaplan-Meier plot of time-to-event from initial dose will be constructed.

		Event	Censor
Time to changing initial 50mg	RAJ1	Dose increase Discontinuation	Study Completion
Time to changing initial 100mg	RAJ3/4	Dose increase Dose decrease Discontinuation	Study Completion
Time to dose increasing initial 100mg	RAJ3/4	Dose increase	Study Completion Discontinuation Dose decrease
Time to dose decrease initial 100mg	RAJ3/4	Dose decrease	Study Completion Discontinuation Dose increase

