7.4.4 Influence of Dose Escalation

In order to evaluate influence of ASP015K dose escalation to 100 mg from 50 mg for subjects who shifted from RAJ1 and dose escalation to 150 mg from 100 mg for subjects who shifted from RAJ3 or RAJ4, the selected efficacy variables (ACR20-CRP and DAS28-CRP) will be analyzed based on the days of first dose increase to 100mg or 150mg until dose decrease. Following intervals will be used.

- o < -336
- o -336 < -252
- o -252 < -168
- o -168 < -84
- o -84 < 0
- 0 < 84
- o 84 < 168
- \circ 168 < 252
- o 252 < 336
- o >= 336

If multiple efficacy values are included in one interval, the last one is used.

- Graphical analysis:
 - ACR20-CRP will be plotted
 - The mean-standard deviation plot of actual values and changes from baseline of preceding study will be presented for DAS28-CRP from baseline of preceding study.

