10 APPENDICES

10.1 Appendix 1: Overview of Efficacy Endpoints

Table below summarizes the analyses of the efficacy variables, with "X" indicating that the variable will be analyzed. All analyses will be based on the FAS and presented by preceding studies, unless otherwise specified. No statistical hypothesis testing will be performed.

Overview of Efficacy Endpoints analysis

		Compone	Component for use			r Analysis		
Analysis	Type/Analysis Variable	CRP	ESR	None	RAJ1	RAJ3	RAJ4	Analysis Group
Categori	cal Variables				1	1	1	_
1.1	Percentage of subjects achieving ACR20/50/70 at each visit	X	X		X	X	X	preceding studies
1.2.1	Percentage of subjects achieving ACR20 at each visit Analysis by Treatment Sequence Set of preceding study	X			X			Treatment Sequence Set
1.2.2	Percentage of subjects achieving ACR20 at each visit Analysis by Treatment Sequence Set of preceding study	X				X		Treatment Sequence Set
1.2.3	Percentage of subjects achieving ACR20 at each visit Analysis by Treatment Sequence Set of preceding study	X					X	Treatment Sequence Set
1.3	Percentage of subjects achieving ACR20 at each visit Analysis of Efficacy in Each Dose Level	X			X	X	X	preceding studies

12-Nov-2019 Astellas Page 57 of 94

		Component for use			Study for Analysis			Analysis Croun
Analysis Ty	/pe/Analysis Variable	CRP ESR None		RAJ1	RAJ3	RAJ4	Analysis Group	
1.4.1	Percentage of subjects achieving ACR20 at each interval Influence of Dose Escalation	X			X			Subjects Who Experienced Dose Up to 100 mg
1.4.2	Percentage of subjects achieving ACR20 at each interval Influence of Dose Escalation	X				X		Subjects Who Experienced Dose Up to 150 mg
1.4.3	Percentage of subjects achieving ACR20 at each interval Influence of Dose Escalation	X					X	Subjects Who Experienced Dose Up to 150 mg

12-Nov-2019 Astellas Page 58 of 94

		Component for use			Study fo	r Analysis		
Analysis	Type/Analysis Variable	CRP	ESR	None	RAJ1	RAJ3	RAJ4	Analysis Group

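### The RAJ1 dose-escalation display in SAP 7.4.4 pools increases made under three different protocol rules, so its level and apparent change depend partly on an unreported mix

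*SAP*

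**What the plan says.** SAP 7.4.4 is the plan's dedicated escalation analysis. Its stated aim begins "In order to evaluate influence of ASP015K dose escalation to 100 mg from 50 mg for subjects who shifted from RAJ1". Time is counted from the first increase, whatever its reason, in 84-day intervals from before -336 to 336 and beyond. SAP Appendix 1 (items 1.4.1 and 10.4.1) takes all RAJ1 subjects who went up to 100 mg as one group.

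The protocol gives three routes to that increase.

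- **Ver. 1.3** (Protocol Appendix 7, synopsis): "Subjects who have no safety problems but show lack of efficacy may later increase the dose to 100 mg/day". The criterion reads "When the DAS28-ESR score is 3.2 or higher (corresponding to moderate disease activity or high disease activity) on the study visit day", at two or more consecutive visits up to Week 12, plus a safety judgement.
- **Ver. 2.0/3.0**: Protocol 2.2.2 says that once the new tablets are available "the dose shall be increased to 100 mg/day, with the exception of the subjects" for whom the investigator considers an increase inappropriate. Protocol 5.1.1 says only that the need for a change is to be assessed, and the synopsis (Test Drug) that the dose may go up on a safety judgement. None of these wordings carries a disease-activity condition.
- **After approval**: for subjects on 50 mg in Japan, "the dose will be increased to 100 mg/day after the NDA approval in Japan" (Protocol 2.2.1; likewise 5.1.2), with withdrawal if that is not possible. RAJ1 was conducted in Japan (Protocol 1.2.4), so this rule reaches the cohort.

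The SAP distinguishes protocol versions only for tablet counts in compliance (SAP 6.5).

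**The concern.** The three routes select different subjects. Route 1 admits only those with DAS28-ESR of 3.2 or higher at the decision, so their pre-increase values are high partly by selection and tend to fall afterwards even without a drug effect. Routes 2 and 3 apply no such selection. A curve that aligns all of them at day 0 starts from a level, and shows a change, that both depend on how many subjects came by each route. A reader would naturally take the RAJ1 display as the response to raising the dose for inadequate effect, and as written it cannot be read that way. SAP 7.4.3 does not fill the gap, because its initial-dose analysis drops data after the first change. The 100 to 150 mg step for RAJ3 and RAJ4 subjects keeps a DAS28-ESR condition (Protocol 5.1.2), so the problem is confined to RAJ1.

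**Working it through.** The plan states no figure on this point, so there is none to reproduce.

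**1. Routes set side by side**

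| Route | Disease-activity condition | Discretion | Where |
|---|---|---|---|
| Ver. 1.3 | DAS28-ESR 3.2 or higher | Permitted, not required | Appendix 7 synopsis |
| Ver. 2.0/3.0, before approval | None | *Shall*, with an exception (2.2.2); *assessed* (5.1.1); *may* (synopsis) | as listed |
| After approval, Japan | None | None; withdrawal if not possible | 2.2.1, 5.1.2 |

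SAP 7.4.4 and Appendix 1 contain no variable for route, version or reason.

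**2. Composition along the time axis**

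The study runs for at most 6 months after approval in Japan (Protocol synopsis). With the SAP's own month length (SAP 6.5), 6 × 30.4375 = 182.6 days, or about 183. Since 182.6 / 84 = 2.17, there is room for two scheduled 12-weekly visits. After a mandated increase a subject can therefore:

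- contribute to all pre-increase intervals, to 0–84 and to 84–168;
- reach only about day 183 of 168–252;
- never enter 252–336 or 336 and beyond.

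Later points can thus move because the set of subjects changes.

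**3. Illustration of direction and rough size**

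These inputs are assumptions, not document figures: subject mean DAS28 3.8, between-subject SD 1.1, within-subject SD 0.5 or 0.7, criterion met when two consecutive scores are 3.2 or higher, and one score used both for selection and for display. With w the criterion-driven share:

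pooled change = w × (change, criterion met) + (1 − w) × (change, criterion not met)

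| Within-subject SD | True effect | Criterion met | Not met | Pooled, w = 75% | Pooled, w = 25% |
|---|---|---|---|---|---|
| 0.5 | -0.5 | -0.57 | -0.40 | -0.52 | -0.44 |
| 0.7 | -0.5 | -0.64 | -0.32 | -0.56 | -0.40 |
| 0.5 | 0 | -0.07 | +0.10 | -0.02 | +0.06 |
| 0.7 | 0 | -0.14 | +0.18 | -0.06 | +0.10 |

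Example: 0.75 × (-0.64) + 0.25 × (-0.32) = -0.56, and 0.25 × (-0.64) + 0.75 × (-0.32) = -0.40.

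- Moving w from 75% to 25% shifts the pooled change by 0.08 (SD 0.5) or 0.16 (SD 0.7).
- It shifts the pre-increase mean from 4.06 to 3.15 or from 4.14 to 3.21, about 0.9.
- Moving the true effect from 0 to -0.5 shifts the pooled change by about 0.5.

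The contrast is deliberately sharp, because everyone outside the criterion class is taken not to meet the criterion. In the study some increases under the later versions may also have been made at 3.2 or higher, which would narrow it.

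**The case against.** The strongest defence is that 7.4.4 is descriptive. Appendix 1 says "No statistical hypothesis testing will be performed", at most 201 subjects are involved (Protocol 7.1), and an uncontrolled before/after display cannot isolate a drug effect whether or not it is split. That stands: restricting to criterion-driven increases leaves regression to the mean and can make it larger (-0.07 to -0.14 above with no true effect). It does not remove the point, because the section has a stated aim and the pooled RAJ1 display does not tell the reader which subjects it describes.

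The later-version increases also cannot all be called automatic. Only Protocol 2.2.2 uses mandatory wording, and an investigator could still have raised the dose for inadequate response after the switch. That stands too, and it is why date alone is not enough to classify an increase.

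Four stronger readings are tempting and not supported.

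- **The Kaplan-Meier curve is wrong as well.** "Time to changing initial 50mg" is an exposure display in SAP 7.3.1. Its event is any increase or discontinuation, so it shows time on the starting dose, and for that quantity every increase is properly an event. It should not be read as time to inadequate response, but the SAP does not offer it as that.
- **That curve will step at an administrative date.** Its axis is time since first dose, and the later versions took effect centre by centre (Protocol synopsis, Design and Methodology). No common step follows.
- **Subjects increased under the later rules had mostly controlled disease.** The ver. 1.3 increase was permissive, so subjects with active disease could still be on 50 mg at the switch. The documents report no disease activity for them.
- **The pooled result reflects the mix and not the drug.** In the illustration it reflects both, and the assumed drug effect moves the change more than the mix does.

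**Conclusion.** The point holds for the RAJ1 part of SAP 7.4.4. The display pools increases that required DAS28-ESR of 3.2 or higher with increases that carried no disease-activity condition and increases that were mandated, so its level and apparent change depend partly on an undisclosed mix. That mix can change across intervals, because follow-up after a mandated increase stops at about 183 days.

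The size cannot be given, because the documents do not say how many of the 201 subjects took each route; the mandated class could be small or empty. The illustration suggests a modest effect on the mean change and a larger one on the pre-increase level, under assumed inputs. Nothing confirmatory is affected. This is about whether the plan's one escalation analysis can be interpreted for RAJ1.

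**What to change.** 1. For each RAJ1 first increase, derive a class from the protocol version in force for that subject at the increase (ver. 1.3; ver. 2.0 or later before approval; after approval) and from whether DAS28-ESR was 3.2 or higher at that visit.
2. Present the 7.4.4 ACR20-CRP and DAS28-CRP displays by class, with n per interval, alongside the pooled display.
3. State in 7.4.4 that these are uncontrolled before/after descriptions in which regression to the mean remains, especially in the criterion-driven class.
4. Keep the 50 mg Kaplan-Meier curve as an exposure display. If reasons are wanted, add cumulative incidence by class of increase and for discontinuation. Censoring at protocol-driven increases would not serve: it would be informative, since subjects left on 50 mg under the later versions are those judged unsuitable for an increase, and discontinuation would still count as an event.
5. Reconcile SAP 3.2, which ends the study at approval, with the protocol's post-approval period and mandated increase, and reconcile the *shall*, *assessed* and *may* wordings in Protocol 2.2.2, 5.1.1 and the synopsis. This review takes no view on which dosing rule is right.

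**Cost.** The class is a derived variable, and no new data collection is needed: dose changes go in the CRF (Protocol 5.1.2), and joint counts, ESR and SGA are scheduled at each visit. The limits are smaller groups, a version-switch date that must be obtained per centre, and the absence of a stated CRF field for the reason for an increase, so the class approximates the reason.

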
Test Drug Mode of Administration: Dose: Duration of Treatment:
	
Test drug: ASP015K 50 mg, 100 mg, and 150 mg tablets Dose: [Subjects who transferred from study RAJ1] The starting dose will be 50 mg/day. [Subjects who transferred from studies RAJ3 or RAJ4] The starting dose will be 100 mg/day.
 
For those subjects who have completed study RAJ1 and are continuing treatment with ASP015K at a dose of 50 mg/day, the need for a change in the dose shall be assessed at the initiation of the clinical study under the protocol ver. 2.0/ver. 3.0. If the dose is not increased to 100 mg, and

- CONFIDENTIAL -

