Treatment	Treatment	Week 0- Week 12	Week 12- Week 28	Week 28- Week 52		
Sequence	Sequence Label					
Code						
SEQ J4-1	100mg	ASP015K 100 mg	ASP015K 100 mg	ASP015K 100 mg		
SEQ J4-2	150mg	ASP015K 150 mg	ASP015K 150 mg	ASP015K 150 mg		
SEQ J4-3	Placebo to 100mg at Week 12	Placebo	ASP015K 100 mg	ASP015K 100 mg		
SEQ J4-4	Placebo to 150mg at Week 12	Placebo	ASP015K 150 mg	ASP015K 150 mg		
SEQ J4-5	Placebo to 100mg at Week 28	Placebo	Placebo	ASP015K 100 mg		
SEQ J4-6	Placebo to 150mg at Week 28	Placebo	Placebo	ASP015K 150 mg		

- o 100 mg: subjects who initially treated ASP015K 100 mg
- o 150 mg: subjects who initially treated ASP015K 150 mg
- Placebo to 100 mg at Week 12: subjects who initially treated Placebo group and switched 100 mg at Week 12 and at least one dose of ASP015K 100 mg drug after switched
- Placebo to 150 mg at Week 12: subjects who initially treated Placebo group and switched ASP015K 150 mg at Week 12 and at least one dose of ASP015K 150 mg drug after switched
- Placebo to 100 mg at Week 28: subjects who initially treated Placebo group and switched ASP015K 100 mg at Week 28 and at least one dose of ASP015K 100 mg drug after switched
- Placebo to 150 mg at Week 28: subjects who initially treated Placebo group and switched ASP015K 150 mg at Week 28 and at least one dose of ASP015K 150 mg drug after switched
- If onset date of AE is Unknown, then missing onset date of AE will be imputed as following steps.
 - 1. If only the day of the month is missing (e.g., 2013-03), then the first day of the month will be used (2013-03-01),
 - 2. If both day and month are missing (e.g., 2013), then the first day of January will be used (2013-01-01).
 - 3. If day, month and year are missing, then the first date of study drug will be used.
 - 4. If imputed onset date of AE is earlier than the first date of study drug, [Adverse Events(From RAJ2) -page of the CRF]

then the onset date of AE will be re-imputed by the same date as the first date of study drug at RAJ2.

[Adverse Events(From RAJ1)/(From RAJ3 or RAJ4) -page of the CRF] then the onset date of AE will be re-imputed by the same date as the first date of study drug at the preceding study.

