7.4.3 Analysis of Efficacy in Initial/Maximum Dose Level

The selected efficacy variables (ACR20-CRP and DAS28-CRP) are summarized by preceding study. In Initial dose analysis, data obtained after changing initial dose at RAJ2 (50mg for subjects from RAJ1, 100mg for subjects from RAJ3/4) will not be used for efficacy analyses.

- Categorical variables at each visit will be summarized.
- For continuous variables, raw value and change from baseline of preceding study at each visit will be summarized by descriptive statistics.

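### SAP 7.4.4, 7.4.3 and the RAJ3/4 curves in 7.3.1 pool subjects who step down from 150 mg at RAJ2 entry with subjects who ended the parent study on 100 mg, so the 7.4.4 before/after display cannot be read as the influence of going from 100 to 150 mg.

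*SAP*

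**What the plan says.** **Starting dose.** The Protocol synopsis states "Subjects who transferred from studies RAJ3 or RAJ4] The starting dose will be 100 mg/day", whatever the parent-study arm. Protocol 2.2.2 gives the reason: "the starting dose for this extension study has been set at 100 mg/day, which was the lower of the two doses" used in Phase III.

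**Where subjects come from.** SAP 7.1 defines Treatment Sequence Sets. In RAJ3 and RAJ4 there are initial arms on each dose (for RAJ4, for example, "150 mg: subjects who initially treated ASP015K 150 mg"). Placebo subjects switch to 100 or 150 mg at Week 12, or in RAJ4 at Week 12 or Week 28. The etanercept group does not enter RAJ2.

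**The three analyses.**
- SAP 7.4.4 plots ACR20-CRP and DAS28-CRP by days from the first increase, to assess "dose escalation to 150 mg from 100 mg for subjects who shifted from RAJ3 or RAJ4". In Appendix 1 the analysis group for items 1.4.2 and 1.4.3, and likewise 10.4.2 and 10.4.3, is "Subjects Who Experienced Dose Up to 150 mg".
- SAP 7.4.3 summarises the same two variables by preceding study. In its initial-dose part, data after a change from the starting dose are dropped ("50mg for subjects from RAJ1, 100mg for subjects from RAJ3/4) will not be used for efficacy analyses"). Appendix 1 items 1.3 and 10.3 are grouped by preceding study only.
- SAP 7.3.1 lists Kaplan-Meier rows for RAJ3/4 together, among them "Time to dose increasing initial 100mg".

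None of these is split by the dose on which the subject left the parent study.

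**The concern.** RAJ2 entry means different things for the two kinds of transfer. A subject whose sequence ended on 100 mg continues on that dose. A subject whose sequence ended on 150 mg has had it for 24 to 52 weeks and is then reduced. If both later go from 100 to 150 mg, the first meets 150 mg for the first time and the second goes back to it.

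Section 7.4.4 presents the change around day 0 as the influence of escalation. In a mixed group, part of that change may be recovery from the entry step-down, and part of the earlier data may reflect response reached on 150 mg. By-visit results on the initial dose (7.4.3) likewise combine continued 100 mg treatment with 100 mg after a reduction. The time-to-increase curve (7.3.1) combines increases after a step-down with increases in subjects who had not had 150 mg. These displays are descriptive, so readers will take their message directly from the plotted groups.

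**Working it through.** The plan gives no figure for the number stepping down, so there is nothing to reproduce. The share can be bounded from the documents.

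**1. Last parent-study dose (SAP 7.1).**
- 100 mg: SEQ J3-1, J3-3, J4-1, J4-3, J4-5.
- 150 mg: SEQ J3-2, J3-4, J4-2, J4-4, J4-6.
- Time on 150 mg before entry: 52 weeks (initial arms), 52 − 12 = 40 weeks, or 52 − 28 = 24 weeks (placebo switchers).

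**2. Arm sizes.** Protocol 1.3 gives Week 0–12 adverse event counts with percentages. Each pair fits only one whole number of subjects.
- RAJ3: placebo 54/101 = 53.5%; 100 mg 59/104 = 56.7%; 150 mg 55/102 = 53.9%.
- RAJ4: placebo 84/170 = 49.4%; 100 mg 89/174 = 51.1%; 150 mg 104/174 = 59.8%.
- Both studies: placebo 271, 100 mg 278, 150 mg 276, total 825.

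**3. Share ending on 150 mg.** Share = (150 mg arm + placebo switched to 150 mg) / total. The placebo split is not stated, so it is varied.
- Initial active arms only: 276/554 = 49.8%.
- Placebo split equally: (276 + 0.5 × 271)/825 = 49.9%.
- All placebo to 100 mg: 276/825 = 33.5%.
- All placebo to 150 mg: (276 + 271)/825 = 66.3%.
- Unequal completion, as an assumption: from an equal start with 70% retention on one dose and 90% on the other, the share is 44% or 56%.

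**4. Planned numbers.** Protocol 7.1 plans about 800 treated subjects, 201 of them from RAJ1. That leaves 800 − 201 = 599 from RAJ3/RAJ4. At one half, about 300 step down. At the limits, 0.335 × 599 ≈ 200 and 0.663 × 599 ≈ 397.

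**5. Where Week 0 falls in 7.4.4.** RAJ3/RAJ4 subjects have no scheduled visit between Week 0 (Day 1) and Week 12 (Day 85), per Protocol Table 1, note v. An increase needs at least 4 weeks on 100 mg and a DAS28-ESR of 3.2 or more at the visit (Protocol 5.1.2), so the first scheduled opportunity is Week 12.
- Increase dated to that visit: Week 0 lies at 1 − 85 = −84 days. If the bins include their lower limit, it is in the bin just before escalation. The Week 12 value, at day 0, goes into the first bin after, so Week 0 is the only scheduled value in that last pre-escalation bin.
- Increase dated one day later: Week 0 lies at 1 − 86 = −85 days, one bin further back, still before escalation.
- With the Day 78 to Day 92 visit window, and the increase dated to the visit, Week 0 lies between −77 and −91 days.

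In every case Week 0 is a pre-escalation value, and 7.4.4 has no rule that excludes it. By the notes to Protocol Table 1, Week 0 is the parent Week 52 visit or a day within 28 days after it. For a former 150 mg subject it therefore stands for the end of 150 mg treatment or the four weeks following.

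**The case against.** **The step-down is already shown.** SAP 7.4.2 presents ACR20-CRP and DAS28-CRP by treatment sequence from parent baseline to the end of RAJ2, so a fall in the 150 mg sequences after entry would be visible. This stands in part. But 7.4.2 uses data at any RAJ2 dose and is not aligned to escalation, so it does not replace a split of 7.4.3 or 7.4.4.

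**Other text might cover it.** SAP 7.1 says the sequence set serves the analysis by preceding study, but within efficacy Appendix 1 assigns it only to items 1.2, 1.8, 10.2 and 10.7. Protocol 7.4 allows parent treatment groups to be considered where needed, but commits to nothing here. The subgroups in SAP 7.8.1 have no prior-dose factor. Maximum dose is an RAJ2 exposure item.

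**The size is easily overstated.** This stands. A reader might infer that half of the subjects in 7.4.4 are returning to 150 mg. The one-half describes parent-study sequences, and the documents give no split of escalators. A reader might also apply the share to every parent-study subject, which ignores the planned total of about 800. Nor can the 150 versus 100 mg gap in RAJ1 Week 12 ACR20 size the effect: that was a 12-week study, its subjects may not use methotrexate in RAJ2 whereas RAJ4 transfers must, and the calculation would assume the whole gap is lost.

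**Carry-over of drug is implausible.** This also stands. The reported half-life is 2.8 to 18.5 hours, and the first scheduled visit after entry is Week 12. The point concerns response status at Week 0, not residual drug. How long response persists after step-down is not documented.

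**These are descriptive displays.** True: no hypothesis tests are planned, and efficacy is pooled within RAJ3 and within RAJ4, not across them. Only the Kaplan-Meier rows combine the two studies.

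**Conclusion.** The point holds and should be corrected. As written, 7.4.4 pools a return to 150 mg with a first exposure to it. For former 150 mg subjects who go up at about Week 12, it also shows the Week 0 value as pre-escalation. The pooled display cannot be read as the influence of going from 100 to 150 mg. The 7.4.3 results have the same mixture, without the timing problem.

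A reader might conclude that none of the three analyses answers its question. That goes too far: the 7.3.1 curves validly describe time to dose change under the protocol. They simply do not distinguish the two groups.

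Size: about half of planned RAJ3/RAJ4 transfers, some 300 of about 600, step down at entry. This assumes an equal placebo split and equal roll-over by dose. Over all possible placebo splits the share is 33.5% to 66.3%, so even the lower limit is a third. The share among escalators, and the effect on ACR20 or DAS28, cannot be derived from the documents. Nothing here questions the choice of starting dose.

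**What to change.** In SAP 7.4.3 and 7.4.4 (Appendix 1 items 1.3, 1.4.2, 1.4.3, 10.3, 10.4.2 and 10.4.3), present RAJ3 and RAJ4 results by last parent-study dose:
- 100 mg: SEQ J3-1, J3-3, J4-1, J4-3, J4-5.
- 150 mg: SEQ J3-2, J3-4, J4-2, J4-4, J4-6.

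Add the same stratification to the RAJ3/4 Kaplan-Meier rows in 7.3.1, beside the combined curves.

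In 7.4.4, do not count the Week 0 value of the 150 mg sequences as a 100 mg pre-escalation value, and label their increase as a return to 150 mg.

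The cost is SAP wording and some additional tables and figures. The sequence codes exist, and no data collection or dosing rule changes. The drawback is smaller groups per display. Escalator numbers are not given, so how small cannot be judged now, and each display should show its number of subjects.
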